### Exclusion Criteria

- Subarachnoid hemorrhage
- Presence of other neurological or psychological disorders affecting motor functions
- Moderate to severe pain in the stroke-affected upper extremity (score > 6 on 10-point visual analog pain scale), while using the movable wheelchair arm rest device
- Severe tone at the affected upper extremity (score > 4 on the Modified Ashworth Spasticity scale)
- Severe aphasia (score of 2 or higher on the NIH stroke scale – question 9). PI may dismiss this criterion if the participant is deemed able to follow all study instructions
- Deficits in vision, language, attention, neglect or other cognitive functions severe enough to interfere with safe operation of wheelchair or the movable wheelchair arm rest device
- Currently pregnant
- Difficulty in understanding or complying with instructions given by the experimenter
- Inability to perform the experimental task that will be studied

**Is eligibility based on age, gender, pregnancy/childbearing potential, social/ethnic group, or language spoken (e.g., English Speakers only)?**

No, Subject Eligibility is not based on these factors

### Pre-Screening for Recruitment

**Will identifiable information be accessed/obtained for the purpose of screening, recruiting, or determining eligibility of prospective subjects?**

Yes

**Pre-Screening Activities (check all that apply):**

Study team will screen medical records

### Medical Records

**IMPORTANT!** Partial waiver of HIPAA authorization is required for screening/recruitment purposes only. Signed authorization obtained prior to further access to PHI.

**Specify Medical Record Source (check all that apply):**

Study team will access their own UCI patients' records and abstract data directly from those records

### Data Points

Provide a **complete list of ALL data points, variables, and/or information that will be collected/recorded (i.e. data abstraction form) for pre-screening/recruitment purposes:**

We will use existing information about the date, type (ischemic or hemorrhagic), and location of stroke, as well as whether it has caused weakness, and the age of the patient.

If the list of variables will be attached as a separate document [i.e. case report form (CRF; eCRF)], enter "See Attached" above and check the confirmation box below.

The list of variables is attached as a separate document

**IMPORTANT!** Under a partial waiver of HIPAA authorization, only the **minimum necessary** information should be accessed for pre-screening/recruitment activities, this includes:

- determining eligibility (i.e., shows an inclusion or exclusion criteria) and
- contacting the subject.

The information should not be further accessed, used, or disclosed above and beyond pre-screening/recruitment activities until a signed consent form (and signed HIPAA authorization, as applicable) is obtained.

**Explain why pre-screening/recruitment activities could not be done without access to the information listed above:**

Research recruitment could not practicably be conducted unless given access to protected health information. This is due to the screening processes to assess the eligibility of the individuals, confirming that they suffered a single or multiple ischemic or hemorrhagic strokes resulting in upper extremity weakness.

---

## Recruitment Methods

**IMPORTANT!** Recruitment materials must adhere to UCI [Recruitment Guidelines](#). Various templates are available here: [IRB Forms](#) → Recruitment Templates.

## Indicate all methods that will be used to recruit subjects for this study:

---

### Recruitment Method:

Flyers/Brochures

### Specify 'Other' recruitment methods:

### Specify Where Posted:

UC Irvine Health Clinical Trial web page, clinicaltrials.gov web page

### Type of Space:

Private (i.e., site/media that allows control of access to content)

**REQUIRED!** Applicable consent documents must include reference to the use of [SONA](#).

**REQUIRED!** The [ClinicalTrials.gov](#) statement must be in all applicable consent documents.

**REQUIRED!** The study listed on the [Center for Clinical Research \(CCR\) Find a Trial](#) web page must be registered on [ClinicalTrials.gov](#)

### Specify how contact information will be obtained:

**Examples:**

- Individuals who are economically, educationally or cognitively disadvantaged
- Physician's own inpatients and/or outpatients
- Students (undergraduate, graduate, and medical students)
- Employees of UCI (administrative, clerical, nursing, lab technicians, post-doctoral fellows and house staff, etc.)

**REQUIRED!**

1. Subjects must be approached with an emphasis that participation is voluntary; and
2. Subjects must be informed in a caring manner that no matter their decision, it will NOT affect:
  - a. Their relationship with UCI
  - b. How their doctor cares for them as a patient or their care at UC Health in general and/or
  - c. How their instructor grades their participation in the course; and
3. The information above in item 2 must be included in applicable recruitment and/or consent documents.

**Specify the precautions taken to avoid compromised objectivity:****IMPORTANT!**

- Colleagues may provide a copy of the consent and other UCI IRB approved materials, but do NOT obtain subjects' consent for the research or act as representatives of the investigators.
- A partial waiver of HIPAA authorization is required to allow a treating physician to obtain verbal permission from a patient to disclose their name and contact information to the study team.

**IMPORTANT!** Colleagues must NOT obtain subjects' consent for the research or act as representatives of the investigators.

**REQUIRED!**

- Upload the recruitment letter to be signed by the treating physician in the Attachments section.
- For Exempt Self-Determinations, maintain on file the recruitment letter to be signed by the treating physician.

**Recruitment Method:**

Clinicaltrials.gov

**Specify 'Other' recruitment methods:**

## Specify Where Posted:

## Type of Space:

**REQUIRED!** Applicable consent documents must include reference to the use of [SONA](#).

**REQUIRED!** The [ClinicalTrials.gov](#) statement must be in all applicable consent documents.

**REQUIRED!** The study listed on the [Center for Clinical Research \(CCR\) Find a Trial](#) web page must be registered on [ClinicalTrials.gov](#)

## Specify how contact information will be obtained:

### Examples:

- Individuals who are economically, educationally or cognitively disadvantaged
- Physician's own inpatients and/or outpatients
- Students (undergraduate, graduate, and medical students)
- Employees of UCI (administrative, clerical, nursing, lab technicians, post-doctoral fellows and house staff, etc.)

### **REQUIRED!**

1. Subjects must be approached with an emphasis that participation is voluntary; and
2. Subjects must be informed in a caring manner that no matter their decision, it will NOT affect:
  - a. Their relationship with UCI
  - b. How their doctor cares for them as a patient or their care at UC Health in general and/or
  - c. How their instructor grades their participation in the course; and
3. The information above in item 2 must be included in applicable recruitment and/or consent documents.

## Specify the precautions taken to avoid compromised objectivity:

### **IMPORTANT!**

- Colleagues may provide a copy of the consent and other UCI IRB approved materials, but do NOT obtain subjects' consent for the research or act as representatives of the investigators.
- A partial waiver of HIPAA authorization is required to allow a treating physician to obtain verbal permission from a patient to disclose their name and contact information to the study team.

**IMPORTANT!** Colleagues must NOT obtain subjects' consent for the research or act as representatives of the investigators.

**REQUIRED!**

- Upload the recruitment letter to be signed by the treating physician in the Attachments section.
- For Exempt Self-Determinations, maintain on file the recruitment letter to be signed by the treating physician.

## HIPAA Authorization

## Does this study involve the creation, use, or disclosure of **Protected Health Information (PHI)** (i.e. access to medical records)?

### List of 18 PHI Identifiers from medical records/clinical encounters:

1. Names
2. Social Security Numbers
3. Dates (including birth date, admission date, discharge date, date of death and exact age if over 89)
4. Medical record numbers
5. Address
6. Health plan numbers
7. Phone numbers
8. Fax numbers
- 9.
10. Email address
11. Account numbers
12. License/Certificate numbers
13. Vehicle ID numbers
14. Device identifiers/Serial numbers
15. Web URLs
16. IP address numbers
17. Biometric identifiers
18. Facial Photos/Images
19. Any other unique identifier

Yes

## Identify the [Health Insurance Portability and Accountability Act \(HIPAA\) Authorization process](#) (**check all that apply**):

Partial waiver of HIPAA authorization requested for screening/recruitment purposes only. Signed authorization obtained prior to further access to PHI.  
Signed HIPAA authorization obtained

---

### Waiver of HIPAA Authorization

The Health Insurance Portability and Accountability Act (HIPAA) and the California Confidentiality of Medical Information Act (CMIA) address medical confidentiality and access to medical information for research studies that use, create, or disclose health care related data and records, termed “personal health information.”

- HIPAA Authorization Waivers: The HIPAA Privacy Standard [[45 CFR 164.512\(h\)\(i\)\(2\)\(ii\)](#)] requires that certain criteria be met in order to grant a waiver of individual authorization for research uses of Personal (Protected) Health Information.

For more information, visit: [Protected Health Information](#).

### Partial Waiver of HIPAA

**A Partial Waiver of HIPAA Authorization is Requested.**

**Does the use or disclosure of personal health information involve **more** than minimal risk?**

No

**Would the granting of the waiver adversely affect privacy rights and welfare of the individuals whose records will be used or disclosed?**

No

**Explain (justify) the answer:**

Information will be protected to avoid any breach of confidentiality and will be used by the research team to find patients with ischemic or hemorrhagic strokes with arm weakness

**Could the research practicably\* be conducted without a waiver of HIPAA authorization?**

No

**Explain why research could **not** be done if authorization was required:**

It is not practicable to ask a considerable number of patients to sign the HIPAA Authorization to review their medical records to confirm eligibility and identify 30 eligible subjects.

**Could the research practicably\* be conducted without access to, use or disclosure of the personal identifiers listed in the PHI question?**

No

**Explain why research could **not** be done without access to, use or disclosure of PHI:**

Research recruitment could not practicably be conducted unless given access to protected health information. This is due to the screening processes to assess the eligibility of the individuals, confirming that they suffered a single or multiple ischemic or hemorrhagic strokes resulting in upper extremity weakness.

**Are the privacy risks reasonable relative to the anticipated benefits of the research?**

Yes

**Describe the risk/benefit analysis performed to explain the answer above:**

: Researchers from the study will store all study records and other information in secure location and only study personnel will have access to it.

**Describe the plan to destroy the personal identifiers at the earliest opportunity, or provide a health or research justification for retaining the identifiers:**

Potential subjects are identified through chart review according to our inclusion and exclusion criteria. A screening log will be created to keep an accounting of prospective patients and their interest in study participation. The screening log will be retained for the duration of the study. The screening log will be stored with a coded identifier on password protected computers and paper forms will be filed securely in a HIPAA approved storage in the Acute Rehab Unit (ARU) or Gross Hall at UCI main campus no longer than 6 years after the completion of the study. The number of patients we screen, number of patients enroll in the study, and the number of patients who do not qualify for the study will be retained (with no patient identifiers) for the NIH reports and manuscripts.

**Describe the plan to protect the personal identifiers from improper use and disclosure (i.e., describe data security methods):**

The screening log for non-participants will be kept in a HIPAA approved storage in ARU or Gross Hall at UCI main campus until the completion of study, when they will be destroyed. All other paper forms will be kept in this secure locked cabinet for no longer than 6 years, at which time, the documents will be physically destroyed by shredder

Provide assurance that the PHI will **not be reused or disclosed** to any other person or entity, except as required by law, for authorized oversight of the research study, or for other research for which the use or disclosure of PHI would be permitted.

As the Lead Researcher, I assure all of the above

---

### Informed Consent Process

Identify the methods of **Informed Consent** or assent process as applicable for each participant population (**check all that apply**):

Paper-based signed informed consent/assent

#### Paper-based Signed Informed Consent

Indicate the paper-based signed informed consent/assent (**check all that apply**):

Signed Informed Consent

**REQUIRED!** Submit the Adult Consent Form, Child **Assent Form** and/or Parental Permission Form in the Attachments section.

### Circumstances of Consent

Indicate the location where the consent process will take place (**check all that apply**):

Private room

**Specify how the research team will assure that subjects, their parents, or their legally authorized representative (LAR) have sufficient time to consider whether to participate in the research:**

Subjects or their LAR will be allowed 'X amount of time' to consider whether to consent

**Specify hours, days or weeks for subjects, parents or their LAR will be allowed to consider whether to consent:**

24 hours

---

### Non-English Speakers

**What type of consent process will be used for **Non-English Speaking Participants**?**

The English version of the consent materials will be translated for non-English speaking participants or their LAR once IRB approval is granted. An interpreter will be involved in the consenting process.

**Indicate how non-English speaking subjects or their LAR will be consented in their language and who will be responsible for interpreting and facilitating the informed consent discussion for the non-English speaking subjects:**

The study team has 24-hour access to a translation service with sufficient medical expertise to discuss the research in this study

---

---

---

---

### Project Locations

**Check all sites where UCI investigator(s) will conduct research activities (e.g., recruitment, informed consent, and research procedures including accessing identifiable, private information about participants):**

UCI Campus Facilities or Sites (e.g. school, lab, etc.)

UCI Health Facilities or Sites (e.g. hospital, clinics, etc.)

---

## **Study Design & Statistics**

## **Include an explanation of the study design (e.g., randomized placebo-controlled, cross-over, cross-sectional, longitudinal, etc.) and, if appropriate, describe stratification/randomization/blinding scheme:**

This is a randomized controlled phase II clinical trial designed to test if use of movable wheelchair arm rest device reduces arm impairment compared to conventional training, in addition to standard rehabilitation therapy.

We will recruit individuals with an acute or subacute stroke from the Acute Rehabilitation Unit at UCI Medical Center to participate in this study. Participants will have arm impairment, which we will confirm with the Upper Extremity Fugl-Meyer Motor Assessment. After baseline evaluation, study participants will be equally randomized into two groups: device group versus control group. Randomization will proceed by block allocation based on time of enrollment.

**Movable wheelchair arm rest device group:** participants in this group will be provided with a wheelchair equipped with movable wheelchair arm rest device and will be trained by training therapists on how to use the device to perform stationery reaching practice and to help them move around using the overground mode. Training therapists can customize the range of motion needed for device's integrated electronics to count a "repetition" based on participant's ability. Once training therapists determine participants are competent to operate the device, they will be instructed to perform stationary reaching practice and to use the device to move around the inpatient facility with supervision from study personnel. A target dose of 1000 device "repetition" per day is encouraged. We estimated this will take about 30 minutes per day of device use at around 1 repetition every 2 second. Once participants are discharged from the unit, they will be allowed to keep the movable wheelchair arm rest devices until their 3-month post stroke follow up visit, the last visit of the study. Participants' utilization of the device will be supervised by therapists who have been trained in the device operation. Tenovi Gateway device will be used to collect the amount of use data. This data will be automatically uploaded to secure web portal through a Tenovi Gateway device, which plugs into the wall at subjects' rooms at the Acute Rehab Unit and subjects' homes. The Teniovi Gateway device will automatically communicates with the exercise repetition counts from the movable wheelchair arm rest through bluetooth, then uploads the data to the web portal through a low-speed cellular data connection.

**Control group:** participants in this group will be given an electronic exercise program designed by training therapists. These exercises will be assigned to the participants electronically using a commercial home exercise program platform commonly used by hospital systems (i.e.: Medbridge). They will be encouraged to exercise for 30 min/day in addition to the regular rehabilitation therapy at ARU. These exercises will be monitored and supervised by therapists who have been trained in the study protocol. Once participants are discharged from the unit, they will be allowed to keep the electronic exercise program until their 3-month post stroke follow up visit, the last visit of the study.

All study participants will receive 3 evaluations from a blinded evaluator: baseline at admission to the ARU, at discharge from ARU, and a 3-month post-stroke follow up visit.

Please see attachment for the schedule of study activities.

## **Is this a study for which a statistical analysis plan is appropriate (e.g. quantitative study design)?**

Yes

## **Describe the statistical methods for the stated specific aims and hypotheses. The analysis plans should match the stated study specific aims and hypotheses:**

All reported data from this study will be disaggregated by sex to test for any potential bias due to this biological variable. Data will be analyzed using modified intention-to-treat analysis. That is, all participants will be included in the analysis if the follow-up assessment is available, regardless of any deviations from the protocol. The effect of treatment on the primary outcome measure will be assessed using a repeated measures analysis of covariance (RM-ANCOVA) to account for any baseline differences between groups or variability in treatment intensity, with follow-up comparisons performed using Bonferroni-corrected t-tests or Wilcoxon rank sum tests if the data violates the assumption of normality. We hypothesize the participants in the movable wheelchair arm rest device group will have significantly greater and clinically meaningful (i.e. >4.25 FM points) reductions in motor impairment than participants in the control group due to the increased dose of UE motor system activation. Using data from the sensors on movable wheelchair arm rest device, we will test if this effect depends nonlinearly on the number of repetitions performed with the device, consistent with recent meta-analyses of forelimb recovery in a rodent model of stroke. That is, we hypothesize that the movable wheelchair arm rest device will provide a benefit only if the dose exceeds a threshold. A key goal is to also identify that threshold (by making a graph for humans like the one for rats), which will enable us to move forward with effective clinical prescription and goal setting with the movable wheelchair arm rest device. Visual analog pain, spasticity, and FAC scores will also be analyzed using RM-ANCOVA to test for significant changes related to use of the device. All analyses will be reviewed by a statistical consultant in the Institute for Clinical and Translational Science at UC Irvine.

**Provide precise definitions of the study endpoints and criteria for evaluation; if the primary outcomes are derived from several measurements (i.e., composite variables) or if endpoints are based composite variables, then describe precisely how the composite variables are derived:**

The endpoint of the study is 3-month post-stroke follow up visit. The primary outcome measure is the Fugl-Meyer Upper Extremity Motor Assessment Score at the 3-month post-stroke follow-up.

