**Multi-Center Studies: If known, indicate the total number of subjects enrolled at ALL sites to date:**

For Rancho Los Amigo Rehab Center: 10 Males and 2 Females - total of 12 participants. For Casa Colinas Rehab Center: 10- males, 13 females - total of 23 participants

---

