## Sample Size Determination:

1. Explain how the overall target sample size was determined (e.g., power analysis; precision estimation). Power analysis should (at least) match the primary outcome/endpoint.
2. Provide justification of the effect size for the primary outcome based on preliminary data, current knowledge/literature and/or cost consideration.
3. If appropriate, provide sample size justification for secondary outcomes.

Based on a power analysis using data from our previous LARA RCT with individuals with subacute stroke (n=19)36, enrolling 29 participants in each group, brings a total of 58 from 2 groups, will provide an 80% chance to demonstrate a significant difference in FM between the device and control at the three-month follow up ( $\alpha = 0.05$ ), assuming a dropout rate of 10%.

---

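### Splitting results by sex does not test whether the treatment effect differs by sex; the plan needs one exploratory arm-by-sex interaction estimate

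*Combined protocol and SAP*

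**What the plan says.** The statistical methods text under Study Design & Statistics opens with the only statement on sex: "All reported data from this study will be disaggregated by sex to test for any potential bias due to this biological variable". The declared purpose is a test, and the declared method is disaggregation. The sentence covers all reported data, so it includes the primary Fugl-Meyer (FM) comparison.

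The primary model is a "repeated measures analysis of covariance (RM-ANCOVA) to account for any baseline differences between groups or variability in treatment intensity". The separate answer on the primary outcome lists Bonferroni-corrected t-tests or rank sum tests, and the answer on secondary analyses lists a repeated-measures ANOVA. None of these names sex, site or an arm-by-sex term. Project Procedures stratifies randomisation by FM level only and adds length of stay as a covariate.

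Sample Size Determination gives the design size ("enrolling 29 participants in each group, brings a total of 58 from 2 groups") and the power ("will provide an 80% chance to demonstrate a significant difference in FM between the device and control at the three-month follow up"), but no effect size or SD.

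The renewal form reports enrolment complete at 37 adults, 22 men and 15 women. By site it gives: "For Rancho Los Amigo Rehab Center: 10 Males and 2 Females - total of 12 participants" and "For Casa Colinas Rehab Center: 10- males, 13 females - total of 23 participants".

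**The concern.** Whether an effect differs by sex is a question about the difference between two effects. Two separate results, each judged on its own, do not answer it. One sex can reach significance and the other miss it simply because both groups are small and one is smaller. Without a specified contrast, a reader of the split tables may take such a pattern as a benefit confined to men or to women. If the within-sex tests are uncorrected, the split also gives two extra chances of a positive subgroup when the device does nothing.

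A second, conditional problem concerns site. Women come mostly from one hospital. If the device effect differs between hospitals, an arm-by-sex estimate would absorb part of that difference.

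The renewal form says that analysis and manuscript preparation are under way, so the wording matters now.

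**Working it through.** **1. The plan's own figure.** The plan has 29 per arm, "assuming a dropout rate of 10" per cent. 29 × 0.9 = 26.1, so about 26 completers per arm; 26/0.9 = 28.9, which rounds up to 29. The dropout step is consistent. The 58 itself cannot be re-derived, because only the source of the effect is named ("Based on a power analysis using data from our previous LARA RCT with individuals with subacute stroke (n=19" participants). Working back from 80% power, two-sided 0.05 (the plan does not state sidedness) and 26 per arm, a t-test implies d = 0.79. Since d is not in the documents, a range of 0.5 to 1.0 is shown.

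**2. Sex by site.** The lead site enrolled 2. Men: 22 − 10 − 10 = 2. Women: 15 − 2 − 13 = 0. Check: 2 + 12 + 23 = 37.

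| Site | Men | Women |
|---|---|---|
| Casa Colina | 10 | 13 |
| Rancho Los Amigos | 10 | 2 |
| UCI | 2 | 0 |

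Casa Colina supplies 13/15 = 87% of women and 10/22 = 45% of men. Fisher's exact test, Casa Colina against the rest, gives p = 0.016. Restricted to the two larger sites it gives p = 0.034.

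**3. Comparing within-sex tests.** Assume the same true d in both sexes, near-even arms within sex (men 11 and 11, women 8 and 7), and a two-sided t-test at 0.05 in each sex. With power p_m in men and p_w in women:

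P(exactly one significant) = p_m(1 − p_w) + p_w(1 − p_m)

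| d | Men | Women | Exactly one | Both |
|---|---|---|---|---|
| 0.5 | 20% | 15% | 29% | 3% |
| 0.75 | 39% | 27% | 45% | 10% |
| 0.79 | 42% | 29% | 47% | 12% |
| 1.0 | 61% | 43% | 51% | 26% |

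At d = 0.79: 0.424 × 0.706 + 0.294 × 0.576 = 0.469. With the planned 52 completers and the same sex mix (men 16 and 15, women 11 and 10), power is 57% and 41%, and exactly one sex is significant in 51%. Full accrual would not have cured this.

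With no effect, at least one sex is significant in 1 − 0.95² = 9.8% of trials if uncorrected. If a Bonferroni correction covered the two sexes it would be 1 − 0.975² = 4.9%.

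**4. The interaction test, and the role of site.** These results come from simulation of the reported 37-person sex-by-site table (8,000 trials per scenario, unit residual SD, no true sex difference).

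- Same effect everywhere (d = 0.79): the split is discordant in 47%, and the arm-by-sex test rejects in 5.0%.
- Adding a 1 SD difference in outcome level between Casa Colina and the other sites: the split is discordant in 43%, and the interaction estimate stays unbiased.
- Arm effect of 1.2 SD at Casa Colina and 0.4 SD elsewhere: without site terms the interaction estimate is biased by about 0.34 SD and rejects in about 7%. A site main effect alone leaves the bias at about a third of an SD. Adding arm-by-site brings the bias to about zero and rejection to about 5%.

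**5. Precision of the interaction.** SE = √(1/11 + 1/11 + 1/8 + 1/7) = 0.67 SD. With 33 degrees of freedom the 95% half-width is 2.03 × 0.67 = 1.4 SD. At 52, SE = √(1/16 + 1/15 + 1/11 + 1/10) = 0.57 SD and the half-width is about 1.1 SD. At 37, 80% power needs an interaction of (1.96 + 0.84) × 0.67 = 1.9 SD.

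**The case against.** Four objections have force.

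- **The plan states no within-sex test.** It gives no alpha and no rule for drawing a conclusion, and the bias it mentions could mean imbalance or a main effect of sex. This stands. A reader might infer that the trial is likely to report a benefit in one sex only. The documents do not support that, because the 29% to 51% depends on a reading rule the plan never states and on an effect size it never gives. Even so, the sentence promises a test and supplies no contrast on any of these readings.
- **Site is not the mechanism.** A reader might infer that the sex-site link is why an identical effect would look like a sex difference. It is not: discordance is 47% with no site effect and 43% with a large one. Site can mimic effect modification only if the arm effect itself varies by site, and nothing in the documents says it does.
- **Multiplicity may be covered.** The plan specifies Bonferroni-corrected follow-up comparisons. Whether these extend to sex is not stated, so 9.8% is an upper figure.
- **The replacement settles little.** No aim or hypothesis concerns sex, the plan has a statistical consultant review all analyses, and a half-width of 1.4 SD exceeds the back-solved main effect of 0.79 SD. That is true, and it is a reason to report an estimate with its interval and no verdict.

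**Conclusion.** The concern holds in a limited form. Disaggregation does not test for a sex difference in treatment effect, and the plan names no contrast that would. If within-sex significance were compared in the enrolled 37, an identical effect would appear in exactly one sex in about 29% to 51% of trials (47% at the back-solved d = 0.79), against about 5% false sex differences from an interaction test. With no effect, up to 9.8% of trials would show at least one significant sex. These figures assume two-sided 0.05, near-even allocation within sex, no loss to follow-up and an assumed d. With 10% dropout the 47% becomes 45%.

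The problem comes from comparing two small subgroups. The sex-site association is a separate and conditional matter: it would confound an arm-by-sex estimate only if the device effect differs between sites. The primary device-control comparison is untouched, so priority is low to moderate.

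**What to change.** - Keep tables by sex as description only, with no within-sex significance claims.
- Replace the promise to test by disaggregation with one arm-by-sex interaction term in the primary model. Report it as an estimate with a 95% CI, labelled exploratory.
- Add a sensitivity analysis with site and arm-by-site terms. A site main effect alone does not remove the confounding described above.
- State that a non-significant interaction does not show equal effects in men and women.
- Because accrual is complete, date this change and describe it as made after enrolment.

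The cost is a few lines of text, one extra model term and one sensitivity model. No new data are needed. The drawback is a wide interval, about ±1.4 SD at 37 and wider with the arm-by-site term.
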